4.4.3. Modified Intent-to-Treat Analysis Set

The Modified Intent-to-Treat (mITT) analysis set includes all participants who received at least one dose of study vaccine and who have pre- and at least one post-vaccination immunogenicity data evaluable by the assay in use with valid results for the relevant timepoint(s). The mITT analysis set will be analyzed according to vaccine assigned.

- Note: The mITT analysis set for re-enrolled participants consists of all re-enrolled participants who received at least one dose of study vaccine and who have pre- and at least one post-vaccination immunogenicity data evaluable by the assay in use with valid results while as a re-enrolled participant. Immunogenicity data for re-enrolled participants will only be listed (i.e., will not be included in the summary tables).

4.4.4. Per-Protocol Analysis Set

The Per-Protocol analysis set includes all eligible randomized participants who receive the correct assigned dose(s) of assigned study vaccine within the predefined window (see Table 4-3), have blood collection with valid immunogenicity results within the predefined window (see Table 4-4) and have no other major protocol deviations expected to affect immunogenicity, as determined by the Sponsor Medical Monitor in a blinded manner.

Table 4-3 Study Vaccine Dosing Windows – Priming Vaccination Period

Visit	Window
Dose 1 Administration (Day 0)	0
Dose 2 (Day 28)	+/- 3 days

Table 4-4 Blood Sampling for SARS-CoV-2 Antibodies and CMI Windows – Priming Vaccination Period

Visit	Window
Day 56	+/- 7 days

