7.4 Analysis Sets

The following analysis sets will be used in the statistical analyses:

Intent-to-Treat (ITT) analysis set: includes all participants who receive at least 1 dose of priming study vaccine (ARCT-021 or placebo). Participants will be analyzed according to the vaccine the participant was randomly assigned to.

Safety analysis set: includes all participants who receive at least 1 dose of priming study vaccine (ARCT-021 or placebo). Participants will be analyzed according to the vaccine received at time of priming or booster vaccination.

Reactogenicity analysis set (RAS): includes all participants who receive any dose of priming study vaccine (ARCT-021 or placebo) and provide at least 1 reactogenicity diary report for the time period evaluated. Participants will be analyzed according to the vaccine received.

Per-protocol analysis set: includes all eligible randomized participants who receive the correct assigned dose(s) of assigned study vaccine within the predefined SAP window, have blood collection within the SAP window, have valid immunogenicity results for the relevant time point(s), and have no other major protocol deviations expected to affect immunogenicity, as determined by the Sponsor Medical Monitor in a blinded manner. All

Arcturus Therapeutics, Inc.
Protocol ARCT-021-04, Version 6.0

ARCT-021
09 March 2022

participants in the per-protocol analysis set will be analyzed according to what study vaccine that was received.

Modified intent-to-treat (mITT) analysis set: includes all participants who received at least one dose of study vaccine and who have pre- and post-vaccination immunogenicity data evaluable by the assay in use with valid results for the relevant time point(s). The mITT analysis set will be analyzed according to vaccine assigned.

CMI subset: includes all participants who have evaluable pre- and post-vaccination CMI data available. The data sets include: CD4+ T-cell responses (background subtracted), CD8+ T-cell responses (background subtracted), and Th1/Th2 CD4+ T-cell responses (background subtracted).

Booster Randomized analysis set: consists of all participants who are randomized to a booster vaccination, regardless of the participant's study treatment status in the study. Participants will be analyzed according to the study vaccine to which they were randomized for receipt of booster vaccine.

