8.2. Analysis of Immunogenicity Primary and Secondary Endpoints

8.2.1. Analysis of primary and secondary immunogenicity endpoints

Total NAbS and BAbS titers will be summarized using descriptive statistics (number of subjects (n), median, minimum and maximum) by each time point in priming vaccination period (Baseline, Days 14, 28, 42, 56, 208) and booster vaccination period (Day 208, 236, Early Termination). Summaries of priming vaccination and booster vaccination periods based on their corresponding mITT and PP analysis sets will be presented separately using the applicable treatment groups (Table 4-1). For the analysis of booster mITT analysis set, summary tables with active boosters pooled (as presented in Table 4-1; e.g., A1, A2, B1, B2, etc.) will also be presented.

The following statistics will be provided in the summary tables and/or figures:

- Geometric mean titer (GMT) with corresponding 95% CI will be provided at each time point. The 95% CIs will be calculated based on the t-distribution of the log-transformed values then back transformed to the original scale for presentation. GMT level and corresponding 95% CI will be plotted at each timepoint in priming vaccination period for mITT analysis set. Plots of the reverse cumulative distribution curves also will be provided by treatment group and visit in priming vaccination period for mITT analysis set.
- Geometric mean fold rise (GMFR) with corresponding 95% CI will be provided at each post-baseline timepoint over baseline. The 95% CIs will be calculated based on the t-distribution of the log-transformed values then back transformed to the original scale for

presentation. GMFR and corresponding 95% CI will be plotted at each timepoint in priming vaccination period for mITT analysis set.

- The number and percentage of subjects with fold-rise ≥ 2 and fold-rise ≥ 4 from baseline (Seroconversion) at each post baseline time points will be tabulated with the 2-sided 95% CI using the Clopper Pearson method at each post-baseline timepoint.
- Seropositivity at a participant level is defined as any detectable antibody level above the lower limit of quantification (LLOQ) for the specific assay and antibody measured at timepoints after baseline. Seropositivity rates will be provided with 2-sided 95% CI using the Clopper-Pearson method at each post-baseline time point.

The definition of seroconversion/seropositivity may depend on assay-specific performance characteristics. The conventions are as follows:

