8.3.2. CMI Analysis

CMI responses will be evaluated for CMI subset using parametric flow cytometry for quantification and phenotyping and cytokine staining for TNF- α , IL-2, IFN- γ , IL-4, and IL-13. Blood sampling will be performed at Days 0, 14, 28, 42, 56, 208, 215, 236, and Early Termination in participants enrolled at centers identified with capabilities for isolation of peripheral blood mononuclear cells (PBMCs). CMI testing will not be performed on participants re-enrolling at Day 98-198 (i.e., placebo participants who re-enter the study to receive ARCT-021 priming vaccinations).

Descriptive statistics (N, mean, SD, min, Q1, median, Q3, max) will be provided for each visit including change from baseline at each timepoint, where CMI results are available for the priming vaccination period (mITT and PP analysis CMI subsets) and booster vaccination period (Booster mITT CMI subset). When summarizing the Early Termination visit, only include observations within the booster vaccination period post day 236. The following CMI responses will be summarized:

- CD4+ T-cell responses background subtracted (combined pools): IFN- γ , TNF- α , IL-2, IFN- γ + TNF- α +, IFN- γ + TNF- α + IL-2+
- CD8+ T-cell responses background subtracted (combined pools): IFN- γ , TNF- α , IL-2, IFN- γ + TNF- α +, IFN- γ + TNF- α + IL-2+

- Th1/Th2 CD4+ T-cell responses background subtracted (combined pools): IFN- γ , IL-4, IL-4+ IL-13+, IFN- γ + / IL4+ IL13+

Box plots will be provided for the following for priming vaccination period (mITT CMI subset): CD4+/CD8+ IFN γ , IL4+IL13+, IFN γ +/IL4+IL13+, Th1/Th2.

Analyses will be performed overall and by age group (younger adults (≥ 18 - < 56 years), older adults (≥ 56 years)) for priming vaccination period (mITT CMI subset).

Summary tables and figures will exclude any data points collected at or after the first occurrence of the following intercurrent events: death, missed second ARCT-021 (if applicable) dose, use of immune-modifying drugs, and study infection. Summary tables and figures will exclude all data from subjects with early (before Day 7), active or prior SARS-CoV-2 infection at first vaccination.

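### The priming Per-Protocol set requires an in-window Dose 2 and a Day 56 sample, so its Day 14 and Day 28 results depend on later events; Days 14, 42 and 208 have no sampling window

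*SAP*

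**What the plan says.** SAP 4.4.4 sets three conditions for the priming PP set.

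- Dosing: participants "who receive the correct assigned dose(s) of assigned study vaccine within the predefined window (see Table 4-3"). Table 4-3 gives Dose 1 at Day 0 and Dose 2 at Day 28 ±3 days.
- Sampling: they must "have blood collection with valid immunogenicity results within the predefined window (see Table 4-4"). Table 4-4, titled "Blood Sampling for SARS-CoV-2 Antibodies and CMI Windows" for the priming period, has one row: Day 56 ±7 days.
- Deviations: they must "have no other major protocol deviations expected to affect immunogenicity, as determined by the Sponsor Medical Monitor in a blinded manner".

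Membership is all or nothing. SAP 5.2 tabulates a missed dosing window or a missed sampling window as reasons for exclusion from the PP set. SAP 5.1 counts one PP set, although it splits the Reactogenicity set by dose.

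SAP 8.2.1 summarises antibody results "by each time point in priming vaccination period (Baseline, Days 14, 28, 42, 56, 208") and adds: "Summaries of priming vaccination and booster vaccination periods based on their corresponding mITT and PP analysis sets will be presented separately". SAP 8.3.2 does the same for cell-mediated immunity, "where CMI results are available for the priming vaccination period (mITT and PP analysis CMI subsets"). The table in SAP 8.4 lists PP and PP-CMI for these outputs without limiting the visits.

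Protocol 7.4 leaves the dosing and sampling windows to the SAP and asks that participants "have valid immunogenicity results for the relevant time point(s"). SAP 4.4.3 keeps the reference to relevant time points for mITT; SAP 4.4.4 omits it for PP.

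**The concern.** A PP table should show the response in people who were treated and sampled as planned up to the visit being reported. Here, someone with a correct Dose 1 and good samples at Days 14 and 28 leaves both tables if Dose 2 is not given in window or the Day 56 sample is missing. Neither event can affect a sample already taken.

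The exclusion need not be random. Under Protocol 4.2.2 a confirmed Grade 3 solicited event bars further doses, and Protocol 1.5 reports a possible slight increase in such events at 7.5 µg compared with 5 µg. Membership can therefore depend on reactogenicity after Dose 1, and can do so differently by arm.

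Day 28 matters because the dose-selection objective names the response 28 days after each priming vaccination. No arm receives a single 5 µg dose as its whole priming series, so Group 2 at Days 14 and 28 gives the only summarised priming-period view of that schedule.

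Two further gaps follow from the same definition. Group 1 and Group 4 participants who miss a placebo Dose 2 are excluded. And at Days 14, 42 and 208 the set provides none of the timing control that a PP set is meant to give.

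**Working it through.** The plan gives no figure to reproduce; the point rests on a definition. I compared the PP conditions with each post-baseline priming visit at which PP results are reported. Visit windows are from SAP Appendix 1.

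| Visit | Relation to Dose 2 | Later events required for PP | PP sampling window | Visit window |
|---|---|---|---|---|
| Day 14 | before | Dose 2 and Day 56 sample | none | ±1 |
| Day 28 | before (blood precedes vaccine) | Dose 2 and Day 56 sample | none of its own; bounded by Dose 2 ±3 | ±3 |
| Day 42 | after | Day 56 sample | none | ±1 |
| Day 56 | after | none | ±7 | ±3 |
| Day 208 | after | none | none | +60 |

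Of five visits, three (Days 14, 28, 42) are conditioned on something later. One (Day 56) has its own PP sampling window, one (Day 28) is bounded indirectly, and three (Days 14, 42, 208) have neither. The PP definition does not cite the Appendix 1 windows, and its ±7 at Day 56 differs from the ±3 there.

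**Missed placebo Dose 2.** SAP Table 13-3 counts a missed second dose as an intercurrent event only where ARCT-021 was assigned, on the ground that missing placebo has no impact. Table 4-3 makes no such exception.

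**Illustration of size (all inputs assumed).** Suppose a share q of an arm is removed for a reason arising after the sample, and those removed have titers r times the rest. On the log scale the full mean is m + q·ln(r) and the PP mean is m, so

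PP GMT / full GMT = r^(−q).

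- q = 2%, r = 1.25: 0.996
- q = 10%, r = 2: 0.933
- q = 20%, r = 3: 0.803

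If those removed have lower titers (r below 1), the PP GMT is too high instead.

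The nearest figure in the documents is in Protocol 1.5: 8 AEs leading to discontinuation among more than 500 ARCT-021 recipients across trials, so at most about 8/500 = 1.6% if each AE is a different person. With q = 1.6% and r = 1.25 to 3, the ratio is 0.996 to 0.983. This covers only the AE route, not missed or late visits, and the type of discontinuation is not stated.

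For scale, at the planned SD of 1.2 (SAP 4.2) and 150 per Study Group, the 95% half-width of a log GMT is about 1.96 × 1.2/√150 = 0.19. The middle scenario above shifts it by 0.10 × ln 2 = 0.07.

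**The case against.** The strongest reply is that this is a deliberate set of series completers. The protocol hands the windows to the SAP, and its reference to relevant time points attaches to valid results, not to dosing; the mITT definition uses the same phrase. The Booster PP set follows the same pattern, with one sampling row at Day 236 ±7. That stands to this extent: the SAP does not plainly contradict the protocol, and the silence of SAP Section 11 is a minor fault. It does not explain why a completers' set is tabulated at visits before the series is complete.

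A reader might infer several stronger things that the documents do not support.

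- **That Day 28 samples are uncontrolled.** Blood is drawn before vaccination on dosing days, so the ±3 window for Dose 2 bounds the Day 28 draw for PP members who follow the schedule.
- **That badly timed draws at Days 14 and 42 must stay in.** Blinded deviation review can remove them, though only by judgement and by dropping the whole participant.
- **That Day 28 is the only clean single-dose read.** Day 14 also precedes Dose 2, and Group 1 receives placebo second, so its later priming visits are single-dose reads of 7.5 µg.
- **That the primary results or the dose choice are affected.** mITT is the primary immunogenicity set; the ANCOVA and Miettinen-Nurminen analyses are mITT only; no hypothesis is tested. The single 5 µg dose had been selected by protocol version 4.0, before this final analysis.

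**Conclusion.** The point holds as a defect in a supportive analysis set. Read literally, SAP 4.4.4 makes PP results at Days 14 and 28 conditional on later dosing and attendance, makes Day 42 conditional on the Day 56 sample, excludes for a missed placebo dose that the SAP elsewhere regards as harmless, and leaves Days 14, 42 and 208 without a PP sampling window.

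The effect reaches only the PP summaries of GMT, GMFR, seroconversion and seropositivity and the PP-CMI tables. Neither its size nor its direction can be derived from the documents, which give neither the share lacking an in-window Dose 2 or Day 56 sample nor how their titers differ. The ratios above are illustrations only. The conclusion assumes that the PP flag is programmed as written; if a visit-level flag was intended, the SAP does not say so. The change is worth making because it is cheap and removes selection on events after the sample.

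**What to change.** Define PP by visit in SAP 4.4.4.

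- **Days 14 and 28:** correct Dose 1 and a valid in-window sample at that visit.
- **Day 42 onward:** in addition, the assigned Dose 2 in window, without excluding anyone for a missed placebo Dose 2, in line with Table 13-3.
- **Table 4-4:** add Day 14 ±1, Day 28 ±3 and Day 42 ±1 from the Schedule of Events, and keep ±7 for Day 56. Day 28 needs its own row because it loses its indirect bound once Dose 2 is no longer required there.
- **Day 208:** state an explicit analysis window. Adopting the +60-day visit window would add almost no timing control.
- **Section 11:** record the change and the reason.

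The cost is one revised table and one flag derived by visit. The downside is a PP N that varies by visit, so each PP table must show its own denominators and SAP 5.1 and 5.2 must report PP counts and exclusion reasons by visit.

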4.4.5. CMI Subset

The CMI subset includes all participants who have evaluable pre- and at least one post-vaccination CMI data available. The data sets include: CD4+ T-cell responses (background subtracted), CD8+ T-cell responses (background subtracted), and Th1/Th2 CD4+ T-cell responses (background subtracted).

Analyses on the CMI subset of the mITT (mITT-CMI) and PP (PP-CMI) analysis sets will be presented (see section 8.4 for more details).

4.4.6. Safety Analysis Set

The Safety analysis set includes all participants who receive at least 1 dose of priming study vaccine (ARCT-021 or placebo). Participants will be analyzed according to the vaccine received.

- Note: The Safety analysis set for re-enrolled participants consists of all re-enrolled participants who receive at least 1 dose of study vaccine while as a re-enrolled participant.

4.4.7. Reactogenicity Analysis Set

The Reactogenicity analysis set (RAS) includes all participants who receive any dose of priming study vaccine (ARCT-021 or placebo) and provide at least 1 reactogenicity diary report for the time period evaluated. Participants will be analyzed according to the vaccine received.

- Note: The RAS for re-enrolled participants consists of all re-enrolled participants who receive any dose of study vaccine while as a re-enrolled participant and provide at least 1 reactogenicity diary report for the time period evaluated.

The following analysis sets will be applicable for the Booster Vaccination Period:

4.4.8. Booster Randomized Analysis Set

The Booster Randomized analysis set consists of all participants who are randomized to a booster vaccination, regardless of the participant's study treatment status in the study.

Participants will be analyzed according to the study vaccine to which they were randomized for receipt of booster vaccine.

- Note: The Booster Randomized analysis set for re-enrolled participants consists of all re-enrolled participants who were randomized to a booster vaccination, regardless of the participant's study treatment status in the study.

4.4.10. Booster Reactogenicity Analysis Set

The Booster Reactogenicity analysis set includes all participants who receive any dose of booster vaccination (ARCT-021, ARCT-145, ARCT-156 or placebo) and provide at least 1 reactogenicity diary report for the time period evaluated. Participants will be analyzed according to the vaccine actually received.

- Note: The Booster RAS for re-enrolled participants consists of all re-enrolled participants who receive any dose of booster vaccination while as a re-enrolled participant and provide at least 1 reactogenicity diary report for the time period evaluated.

4.4.11. Booster Intent-to-Treat Analysis Set

The Booster Intent-to-Treat (Booster ITT) analysis set includes all ITT participants who receive at least 1 dose of booster study vaccine (ARCT-021, ARCT-145, ARCT-156 or placebo) or have immunogenicity data collected in the period following booster administration. If a participant did not receive a booster dose but has immunogenicity data collected for the booster vaccination period, the participant is summarized with the placebo booster group. Participants will be analyzed according to the vaccine assigned.

4.4.12. Booster Modified Intent-to-Treat Analysis Set

The Booster Modified Intent-to-Treat (Booster mITT) analysis set includes all mITT participants who has at least one immunogenicity data evaluable by the assay in use with valid results during the booster vaccination period. Participants will be analyzed according to the vaccine assigned. If a participant was not randomized to a booster dose on the Day 208 visit but has immunogenicity data collected during the booster vaccination period, the participant will be summarized with the placebo booster group.

- Note: The Booster mITT analysis set for re-enrolled participants consists of all re-enrolled participants who has at least one immunogenicity data evaluable by the assay in use with valid results during the booster vaccination period while as a re-enrolled participant. Immunogenicity data for re-enrolled participants will only be listed (i.e., will not be included in the summary tables).

4.4.13. Booster Per-Protocol Analysis Set

The Booster Per-Protocol (Booster PP) analysis set includes all eligible randomized participants who receive the correct assigned dose(s) of assigned study vaccine (including booster vaccine) within the predefined window (see Table 4-5), have blood collection with valid immunogenicity results within the predefined window (see Table 4-6) and have no other major protocol deviations expected to affect immunogenicity, as determined by the Sponsor Medical Monitor in a blinded manner. All participants in the Booster per-protocol analysis set will be analyzed according to the study vaccine that was received.

Table 4-5 Study Vaccine Dosing Windows – Booster Vaccination Period

Visit	Window
Booster (Day 208)	No Window

Table 4-6 SARS-CoV-2 Antibodies and CMI Blood Sampling Windows – Booster Vaccination Period

Visit	Window
Day 236 (28 days post-booster vaccination)	+/- 7 days

4.4.14. Booster Cell-Mediated Immunity Analysis Subset

The Booster CMI analysis subset includes all priming period CMI analysis subset participants who has at least 1 CMI data evaluable during the booster vaccination period. The data sets include: CD4+ T-cell responses (background subtracted), CD8+ T-cell responses (background subtracted), and Th1/Th2 CD4+ T-cell responses (background subtracted).

Analyses on the Booster CMI subset of the Booster mITT (Booster mITT-CMI) analysis set will be presented (see section 8.4 for more details).

4.5. Treatment Misallocation

In a blinded fashion, it was determined that there are 4 scenarios observed for 5 participants in the final data with treatment misallocation where the vaccine combination/sequence received differs from the randomized treatment group:

Randomized Treatment Group (Priming Vaccination)	Treatment Misallocation Details	Treatment Group to be Used for Safety Set and Reactogenicity Set for Priming Vaccination
7.5 µg ARCT-021 Single Dose	Non-placebo received at Dose 2	7.5 µg ARCT-021 Two Dose
7.5 µg ARCT-021 Two Dose	Placebo received at Dose 2	7.5 µg ARCT-021 Single Dose
5.0 µg ARCT-021 Two Dose	Placebo received at Dose 2	7.5 µg ARCT-021 Single Dose
7.5 µg ARCT-021 Single Dose	Placebo received at Dose 1*	Placebo

* Note that it was confirmed placebo was received at Dose 2 as planned.

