All CIs will be 2-sided and performed using a 5% significance level. No multiplicity adjustment will be made for this study where multiple treatment groups and endpoints are being evaluated.

All analyses adjusting for age group (≥ 18 to <56 years; ≥ 56 years) will use the values derived from age reported in the interactive response technology (IRT) which was used for randomization stratification.

Early termination visits will be summarized separately for the priming vaccination period and the booster vaccination period, respectively.

Analysis will be presented by study phase and study treatment group where applicable as per [Table 4-1](#) below:

Table 4-1 **Study Phase and Study Treatment Groups**

Study Phase	Study Treatment Groups	Shell Presentation of Treatment Group
Priming Vaccination	ARCT-021 7.5 µg - Placebo	A
	ARCT-021 5.0 µg - ARCT-021 5.0 µg	B
	ARCT-021 7.5 µg - ARCT-021 7.5 µg	C
	Placebo	D
Booster Vaccination	ARCT Priming - ARCT-021 Booster	E1
	Placebo Priming - ARCT-021 Booster	E2
	ARCT Priming - ARCT-154 Booster	F1
	Placebo Priming - ARCT-154 Booster	F2
	ARCT Priming - ARCT-165 Booster	G1
	Placebo Priming - ARCT-165 Booster	G2
	ARCT Priming - Placebo/No Booster	H1
	Placebo Priming - No Booster	H2
Priming Vaccination (Re-enrolled Subjects Only)	ARCT-021 7.5 µg - Placebo	A
	ARCT-021 5.0 µg - ARCT-021 5.0 µg	B
	ARCT-021 7.5 µg - ARCT-021 7.5 µg	C

For some summary tables of booster vaccination period, active boosters will be pooled, and treatment groups will be presented like the following:

Booster Vaccination	ARCT-021 7.5 µg - Placebo - ARCT Booster	A1
	ARCT-021 7.5 µg - Placebo - Placebo Booster/ No Booster	A2
	ARCT-021 5.0 µg - ARCT-021 5.0 µg - ARCT Booster	B1
	ARCT-021 5.0 µg - ARCT-021 5.0 µg - Placebo Booster/No Booster	B2
	ARCT-021 7.5 µg - ARCT-021 7.5 µg - ARCT Booster	C1
	ARCT-021 7.5 µg - ARCT-021 7.5 µg - Placebo Booster/No Booster	C2
	Placebo - ARCT Booster	D1
	Placebo - No Booster	D2

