9.5. Physical Examinations and Emergency Room and/or Hospitalization for COVID-19 Assessment

Listings of complete physical examinations and symptom directed physical examination will be provided. Listings of emergency room visits and/or hospitalization for COVID-19 assessment will be provided.

10. Interim analyses

Three interim analyses will be performed.

- The first interim analysis will focus on safety and will evaluate available safety data for all participants who were initially enrolled as of 05 February 2021 when they have completed Day 7 or Early Termination visit procedures.
- The second interim analysis will evaluate available safety and immunogenicity data for all participants who were initially enrolled as of 05 February 2021 and when they have completed Day 28 or Early Termination visit procedures.

- The third interim analysis will evaluate available safety and immunogenicity data for all participants after they have completed Day 56 or Early Termination visit procedures.

At each of these interim analyses, the datasets from immunogenicity assessments may not contain all participants' data. However, the data cuts outlined above are intended to inform additional clinical development considerations, including selection of ARCT-021 dose for booster administration and selection of final dose and schedule for ARCT-021 administration in the Phase 3 study. The data will be monitored prior to and the database will be locked after the third interim analysis to inform an interim clinical study report.

All available safety and immunogenicity data will be summarized. Blinded data will be shared with the SRC and unblinded data will be shared with the DSMB and sponsor.

Please note that a dry run of safety analysis TLFs will be delivered unblinded to sponsor before the final analysis (i.e., prior to final database lock).

11. Change from Planned Analysis

1. Protocol Section 2.3 states the following exploratory objective: *“To evaluate cell-mediated immune (CMI) responses in participants receiving ARCT-021, ARCT-154, and ARCT-165 versus placebo for priming vaccination”*. This exploratory objective has been revised in SAP section 2.3. to the following: *“To evaluate cell-mediated immune (CMI) responses in participants receiving ARCT 021 versus placebo for priming vaccination.”*
 - Justification: ARCT-154 and 165 are not given as priming vaccinations. This update is to clarify the intent of this exploratory analysis.

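### SAP 4.5 counts 1 or 2 participants randomised to 5.0 µg two-dose as 7.5 µg single dose; unless their first injection was 7.5 µg, this breaks the as-received rule in the Dose 1 safety tables

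*SAP*

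**What the plan says.** SAP 4.5 reports "4 scenarios observed for 5 participants in the final data with treatment misallocation", described as cases "where the vaccine combination/sequence received differs from the randomized treatment group". A table of four rows gives, for each scenario, the randomised group, the misallocation, and the group to be used for the priming Safety and Reactogenicity sets. The third row, with its three cells run together, is "5.0 µg ARCT-021 Two Dose Placebo received at Dose 2 7.5 µg ARCT-021 Single Dose".

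The group definitions are in SAP 3.1, Table 3-1, and in SAP Section 4, Table 4-1. The 5.0 µg group is "ARCT-021 5.0 µg - ARCT-021 5.0 µg" and the 7.5 µg single-dose group is "ARCT-021 7.5 µg - Placebo". No priming group is 5.0 µg followed by placebo.

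For the Safety set, SAP 4.4.6 states the rule: "Participants will be analyzed according to the vaccine received". SAP 4.4.7 applies the same rule to the Reactogenicity set, and Protocol 7.4 agrees for both.

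SAP 9.1.1 tabulates solicited events separately for each vaccination. SAP 9.1.2.1 tabulates unsolicited events after Vaccination 1 and Vaccination 2 by the four priming groups. SAP 5.1 lists the Reactogenicity Set for Dose 1 and for Dose 2 as separate sets.

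**The concern.** On the facts listed in the third row, no 7.5 µg injection was given, yet the participants are labelled with a 7.5 µg regimen. The label names a strength that appears neither in the randomised sequence nor in the listed deviation. No other row does this.

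Safety and reactogenicity are a primary objective. Choosing dose and schedule from the data after each priming vaccination is another (SAP 2.1). Protocol 1.5 already remarks on a possible slight excess of Grade 3 solicited events at 7.5 µg compared with 5 µg. A Dose 1 table by group is where that contrast is read, so counting a 5.0 µg recipient's first-injection events under 7.5 µg puts them on the wrong side of it. The same label also carries into the Vaccination 2, overall-priming and Safety-set demographic tables.

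**Working it through.** **1. How many people.** Five participants fall into four scenarios, each with at least one. Four are used up at one per row and the fifth can be in any row, so row 3 holds 1 or 2. The table has four rows, which agrees with the stated four scenarios.

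**2. The four rows side by side.**

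| Row | Randomised sequence | Listed deviation | Label assigned | Does the label fit the listed facts? |
|---|---|---|---|---|
| 1 | 7.5 µg, placebo | something other than placebo at Dose 2 (strength not given) | 7.5 µg two-dose | Yes at Dose 1; Dose 2 strength not stated |
| 2 | 7.5 µg, 7.5 µg | placebo at Dose 2 | 7.5 µg single dose | Yes at both doses |
| 3 | 5.0 µg, 5.0 µg | placebo at Dose 2 | 7.5 µg single dose | Not at Dose 1; yes at Dose 2 |
| 4 | 7.5 µg, placebo | placebo at Dose 1 | Placebo | Yes at both doses |

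Row 4 has a footnote on the other injection: "Note that it was confirmed placebo was received at Dose 2 as planned". Row 3 has no note on Dose 1.

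**3. Table by table for row 3, if Dose 1 was 5.0 µg.**
- Reactogenicity Set (Dose 1) and Vaccination 1 unsolicited events: the 5.0 µg column is an exact fit and the 7.5 µg column is not.
- Reactogenicity Set (Dose 2) and Vaccination 2 unsolicited events: the injection was placebo. The 7.5 µg single-dose group received placebo at Dose 2, but its first dose differs. The 5.0 µg two-dose group matches at Dose 1 only.
- Overall-priming and Safety-set demographic tables: no group has the sequence 5.0 µg then placebo.

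**4. Size.** Taking m people out of a column of n changes any percentage in it by at most 100 × m/n points. The limit is reached when only the movers had the event, or when everyone except the movers had it. The planned size is 75 per group per age cohort (SAP 4.2), so 150 per group.

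| n | m = 1 | m = 2 |
|---|---|---|
| 150 (group) | 1/150 = 0.67 | 2/150 = 1.33 |
| 75 (age cohort) | 1/75 = 1.33 | 2/75 = 2.67 |

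The receiving column changes by at most m/(n+m): 2/152 = 1.32 points for a group.

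Protocol 1.5 gives 579 enrolled. If these were split equally (an assumption), n is about 579/4 ≈ 145 per group and 579/8 ≈ 72 per cohort. The limits become 0.69 and 1.38, and 1.39 and 2.78.

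**5. Two illustrations.**
- A common event, 130/145 (about 90%) in the 5.0 µg column. Removing one person who had it gives 129/144, a fall of 0.07 points. Removing one who did not gives 130/144, a rise of 0.62 points.
- An event otherwise unseen. 0/150 has a Clopper-Pearson 95% interval of 0 to 2.4%. Two relabelled cases make it 2/152 = 1.3%, interval 0.2 to 4.7%. The intervals overlap widely.

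**6. Denominators.** Start from 150 per group and let row 3 hold two people and the other rows one each. SAP 4.5 then gives 151, 148, 150 and 151 for 7.5 µg single, 5.0 µg two-dose, 7.5 µg two-dose and placebo. Using the 5.0 µg column at Dose 1 gives 149, 150, 150 and 151.

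**The case against.** **The strength at Dose 1 is inferred from silence.** The scenarios were identified in a blinded fashion, and row 1 does not give the strength received either, so the table is not a full record of what was injected. This stands. The contradiction is conditional, and the first step is to state the facts.

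**The label may be a nearest-regimen choice.** SAP 4.5 classifies by the sequence received, and the only group with active vaccine followed by placebo is 7.5 µg single dose. Row 2 treats the same deviation the same way. Any of the four labels misdescribes 5.0 µg then placebo in some respect. For Vaccination 2 and overall tables this stands as a possible convention, though an unexplained one. It fails for Dose 1, which is tabulated on its own and where a fitting column exists.

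**Moving these people to the 5.0 µg column throughout would break the same rule.** After Dose 2 it would put placebo recipients unmarked in a column of active second doses. This stands, and it limits the remedy.

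**Section 11.** A reader might infer from row 3's absence from "Change from Planned Analysis" (SAP Section 11) that it is an undeclared departure. The documents do not support that. None of the four misallocation rows appears there, and the rule is openly set out in SAP 4.5.

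**Visibility.** SAP 7.3 summarises whether each dose was given per protocol, SAP 5.2 summarises significant and major deviations, and both provide listings. The cases are therefore traceable. Nothing in those descriptions says that a safety table would show the strength received, and the table shells are not in the documents.

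**Conclusion.** The point holds in a limited form. If Dose 1 was 5.0 µg, row 3 conflicts with SAP 4.4.6 and 4.4.7 in the Dose 1 solicited and Vaccination 1 unsolicited tables. In the later tables the label is unexplained rather than shown to be wrong.

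The effect is minor: 1 or 2 people, with limits of 0.7 or 1.3 points per planned group and 1.3 or 2.7 per planned age cohort. Actual group sizes are not given.

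Two stronger readings are tempting. One is that the row is a proven misclassification; the SAP does not record the Dose 1 strength, so this cannot be said. The other is that it distorts the comparison of 5.0 with 7.5 µg or the choice of dose. The figures do not support that. No conclusion about the ordering of the groups turns on 1 or 2 people, Protocol 7.2 plans no hypothesis tests, and Protocol 7.8 shows the Phase 3 dose already selected. The mITT immunogenicity analyses follow the assigned vaccine (SAP 4.4.3) and are unaffected.

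**What to change.** In SAP 4.5, give the product and strength received at Dose 1 and at Dose 2 for every row, including row 1. Then reconcile row 3 with SAP 4.4.6 and 4.4.7:

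- If Dose 1 was 7.5 µg, say so and keep the label.
- If Dose 1 was 5.0 µg, count these participants in the 5.0 µg column for Vaccination 1 safety and Reactogenicity Set (Dose 1). For Vaccination 2, Reactogenicity Set (Dose 2), overall-priming and Safety-set demographic tables, show them as a separate row or column for 5.0 µg then placebo. Alternatively, keep a four-group label as a stated convention, with a footnote giving the sequence received. Do not place them unmarked in either the 7.5 µg single-dose or the 5.0 µg two-dose column.

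The cost is two entries per row in one table and either a footnote or one small extra row. Group denominators would differ by 1 or 2 between Dose 1 and later tables. No new data collection or statistical method is needed, and nobody leaves the Safety set.
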